19.1. Primary Objectives

19.1.1. Primary Safety Objective

Objective

The Attain Stability Quad MRI SureScan LV Lead (Model 4798) will be considered safe if the probability of subjects free of Model 4798 lead-related complications at 6 months post-implant is greater than 87% (i.e., the lower bound of a one-sided 97.5% confidence interval must be greater than 87%).

Hypothesis:

$$H_0: S_{(6\text{-month})} \leq 87\%$$

$$H_1: S_{(6\text{-month})} > 87\%$$

where $S_{6\text{-month}}$ is the probability that a subject remains free from Model 4798 lead related complications through 6 months since implant.

Endpoint Justification

The study primary safety endpoint is Attain Stability Quad MRI SureScan LV Lead (Model 4798) related complications. All reported system and procedure-related AEs will be reviewed by an event review committee for LV lead relatedness and severity (see Section 18.1).

Utilizing lead related complication free survival probability to evaluate lead safety performance is widely accepted across cardiac device manufacturers and in the medical literature. Current already market-released Quadripolar LV lead 6-month safety performance is summarized in Table 16. The population performance of the Attain Stability Quad MRI SureScan LV Lead (Model 4798) is expected to be similar to the Medtronic Attain Performa Model 4298 lead.

Table 16: Safety Performance of Market Released Quadripolar Lead

	Medtronic Attain Performa²⁰	St. Jude Medical Quartet²²	Boston Scientific ACUIITY X4²³
6-month LV Lead Complication Free Survival Probability Estimate	Model 4298 (Canted): 96.0% Model 4398 (Straight): 98.8% Model 4598 (S-shape): 96.2%	96% at 3 months	Straight: 96.5% Spiral: 98.5%

[figure not shown]
Statistical Analysis Methods

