The primary objective will be analyzed using the time-to-first event Kaplan-Meier survival analysis method. Time 0 will be the day a subject undergoes the implant procedure of a Attain Stability Quad MRI SureScan LV Lead (Model 4798), which will be independent of success status of this implant procedure. Event date is the onset date of a subject's first complication that is related to the Attain Stability Quad MRI SureScan LV Lead (Model 4798) according to CEC adjudication. Subjects who undergo an Attain Stability Quad MRI SureScan LV Lead (Model 4798) implant attempt and do not experience any LV lead related complications will be censored at the time of their last known exposure to the Attain Stability Quad MRI SureScan LV Lead (Model 4798) for the survival analysis. For any lost-to-follow up subject, the last contact date will be used as the censor date. The 1-sided 97.5% confidence limit lower bound for the survival probability at 6 months (183 days) will be calculated using the log-log survival function approach (Kalbfleisch and Prentice 2002).

Sample Size Consideration

The primary safety objective performance criterion is set to be identical to Medtronic's Attain Performa Clinical Study (IDE Number: G120213). Therefore, the sample size calculation assumptions are derived based on the Model 4298 lead study results. The Attain Performa Model 4298 lead reported a 6-month complication free survival probably of 96.0%, with 97.5% Confidence Lower Limit of 94.3% (PMA-s clinical report).

The binomial calculation (Z-test) is used for initial sample size estimation. In order to preserve the overall study power, a type II error less than 10% was used for the sample size calculation. A sample size of 170 subjects completing their 6-month visit achieves greater than 90% power to detect a difference of 7% using the one-sided binomial test. The target significance level is 0.025. These results assume that the population proportion under the null hypothesis is 87% with an expected value of 94% (Figure 5). To account for 15% attrition, the enrollment size for this objective is 200.

Figure 5: Primary Safety Objective Sample Size Consideration by Difference Performance Assumption**Determination of Patients / Data for Analysis**

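### For the primary safety objective, 170 completers give about 86% power under the planned success rule, not the stated more than 90%; the planned 400 completers are unaffected

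*Protocol*

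**What the plan says.** Protocol section 19.1.1 (Primary Safety Objective) gives every input needed to check its power statement.

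- **Success rule.** The lead is considered safe if "the lower bound of a one-sided 97.5% confidence interval must be greater than 87" percent.
- **Planned analysis.** Kaplan-Meier estimation, where the "lower bound for the survival probability at 6 months (183 days) will be calculated using the log-log survival function approach".
- **Sizing assumptions.** "the population proportion under the null hypothesis is 87% with an expected value of 94" percent, and "The target significance level is 0.025".
- **Target.** To protect overall study power, "a type II error less than 10% was used for the sample size calculation".
- **Result claimed.** "A sample size of 170 subjects completing their 6-month visit achieves greater than 90% power to detect a difference of 7" percentage points, attributed in the same sentence to the one-sided binomial test.

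The section calls the sizing method a binomial Z-test used for initial estimation. It does not say which variance the Z-test uses. It then inflates 170 for 15% attrition to 200 enrolled. Table 18 (Overall Study Sample Size Requirements) carries 170 and 200 as the required numbers for this objective, next to an overall requirement of 400 at 6 months and 471 enrolled.

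**The concern.** All inputs are fixed in one paragraph, so the power can be recomputed without the SAP, and the usual calculations fall short of 90%. The other two primary objectives do reproduce under the exact binomial test. Efficacy objective #1 (145 subjects, 80% against 90%) gives 91.3% where 91% is stated. Efficacy objective #2 (50 subjects, 80% against 97%) gives 98.3% where 98% is stated. The safety figure is the one that does not fit.

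What is at stake is the accuracy of a stated justification for a primary objective in an IDE protocol. A reviewer who repeats the calculation with the named binomial test, or with the log-log bound that decides success, will not obtain the stated power. Table 18 also lists 170 as the number this objective needs, which is not true at the 10% type II error the protocol sets for itself.

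**Working it through.** **Inputs** (all from section 19.1.1): p0 = 0.87, p1 = 0.94, one-sided α = 0.025 (z = 1.96), n = 170 completers. Censoring is set aside, because the protocol's statement is about subjects who complete the 6-month visit.

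**1. Looking for the stated figure.** A Z-test with the estimated variance rejects when (x/n − 0.87) / √[(x/n)(1 − x/n)/n] ≥ 1.96.
- x = 155: 1.92, does not reject.
- x = 156: 2.26, rejects.

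The cut-off is 156, and P(X ≥ 156 | 170, 0.94) = 0.912. This reproduces "greater than 90%". The true one-sided error of the rule is P(X ≥ 156 | 170, 0.87) = 0.0357, above 0.025.

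**2. Exact binomial test.** Find the smallest x with P(X ≥ x | 170, 0.87) ≤ 0.025.
- x = 156: 0.0357, too large.
- x = 157: 0.0196, acceptable.

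The power is P(X ≥ 157 | 170, 0.94) = 0.8562, and the type II error is 1 − 0.8562 = 0.144.

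**3. Z-test with null variance.** This rejects when (x/n − 0.87) / √(0.87 × 0.13/n) ≥ 1.96.
- x = 156: 1.85, does not reject.
- x = 157: 2.08, rejects.

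The cut-off and power are the same as in step 2. The closed form agrees:

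Φ{[0.07√170 − 1.96√(0.87 × 0.13)] / √(0.94 × 0.06)} = Φ(1.07) = 0.857.

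**4. Planned log-log bound.** Without censoring, S = x/n and Greenwood's variance of log S is (1 − S)/(nS). The lower bound is S^exp(1.96 √[(1 − S)/(nS)] / |log S|).
- x = 156: bound 0.865, not above 0.87, fails.
- x = 157: bound 0.872, above 0.87, passes.

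The power is again 0.8562. The 156 of 170 that the Wald rule accepts would fail the protocol's own success criterion.

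| Test at n = 170 | Cut-off | True one-sided error | Power |
|---|---|---|---|
| Exact binomial | 157 | 0.0196 | 0.856 |
| Z, null variance | 157 | 0.0196 | 0.856 |
| Log-log bound, no censoring | 157 | 0.0196 | 0.856 |
| Z, estimated (Wald) variance | 156 | 0.0357 | 0.912 |

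**5. Sizes that would reach 90%.** Power against n is saw-toothed, so the answer depends on the convention used.
- Log-log bound: first reaches 90% at 187 (0.902), falls back, is above 90% again at 196 to 201, is last below it at 205, and stays above from 206.
- Exact test: first reaches 90% at 186 and stays above from 205.
- Closed-form null-variance Z: 190.

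**6. At the planned study size.** With 400 completers the exact and log-log cut-off is 362, and power at 94% is 0.998.

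**The case against.** The strongest reply is that nothing operational depends on the figure. Section 19 says the objectives are analysed once the Table 18 requirements for all primary and secondary objectives are met, and the overall requirement is 400 at 6 months. The safety test is therefore not planned at 170, and at 400 its power is about 99.8%. This stands, and it limits the point to a correction of the stated justification.

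A second reply is that the protocol names a Z-test, labels the estimate initial and calls 0.025 a target, so the figure comes from an approximation and is not a slip in arithmetic. That is fair as to its origin. The Wald form is an inference, since the variance is not stated and Figure 5, cited for these assumptions, is not available here. It does not rescue the claim. The same sentence credits the power to the binomial test, the null-variance Z-test gives 86%, and the log-log rule that decides success gives 85.6%.

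Third, Kaplan-Meier uses partial follow-up from dropouts, so 200 enrolled carry more information than 170 completers. Full information on 200 would give 90.5%. Also, 94% is cautious next to the 96.0% reported for Model 4298, and at 96% a sample of 170 has 99.1% power. Both are true, but the protocol's sentence concerns 170 completers at 94%.

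Two stronger readings are tempting. A reader might multiply the three objective powers, 0.856 × 0.913 × 0.983 ≈ 0.77, and infer that overall study power is 77%. No planned analysis has that power, because all three objectives are read from the same study of about 400 completers, not at 170, 145 and 50. A reader might also conclude that Table 18 must show 206. That number follows only from requiring power above 90% at every larger n, a rule the protocol never states.

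**Conclusion.** The claims of more than 90% power and a type II error below 10% are wrong for 170 completers under the planned success rule. Power is 85.6% and the type II error is 14.4%. This rests on the protocol's own inputs and on no censoring among completers. Of the tests tried, only a Wald Z-test with a true one-sided error of 3.6% exceeds 90%, and it is not the planned analysis.

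The documents do not support reading this as an underpowered study. Total enrollment, the decision rule and the power at the planned 400 completers (about 99.8% if the true rate is 94%) are unchanged. It is worth correcting because it misstates the basis of a primary objective and can be checked from one paragraph.

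**What to change.** In section 19.1.1, state that 170 completers (200 enrolled at 15% attrition) give about 86% power for 87% against 94% under the exact or log-log method, and that the planned 400 completers give about 99.8%. Remove the claims of more than 90% power and of a type II error below 10% for 170.

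If the safety column of Table 18 is meant to show a size that meets 90%, recompute it with the planned log-log or exact method and state the convention. With the log-log bound, for example, power first reaches 90% at 187 completers and stays above it from 206. Otherwise, leave 170 and 200 in the table and attach the corrected power to them.

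The cost is a few sentences and at most two table cells. No patients are added, because 400 at 6 months already governs.

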19.1.2. Primary Efficacy Objective #1**Objective**

The Attain Stability Quad MRI SureScan LV Lead (Model 4798) will meet the first primary efficacy objective if the proportion of subjects with at least one Attain Stability Quad MRI SureScan LV Lead (Model 4798) pacing vector having a pacing capture threshold (PCT) less than or equal to 2.5 V at 0.5ms pulse width (with absence of PNS at 5.0 V) at 6 months post-implant is greater than 80% (i.e., the lower bound of the one-sided 97.5% confidence interval must be greater than 80%).

Hypothesis

$H_0: P_{1_{6\text{-month}}} \leq 80\%$

$H_A: P_{1_{6\text{-month}}} > 80\%$,

[figure not shown]
where $P_{1_{6\text{-month}}}$ is the proportion of subjects with pacing voltage thresholds $\leq 2.5\text{V}$ at 0.5ms (with absence of PNS at 5.0 V) at 6 months follow-up visit post-implant for at least one LV lead pacing vector.

Endpoint Justification

The Attain Stability Quad MRI SureScan LV Lead (Model 4798) is equipped with the identical four electrodes to the Attain Performa LV leads. At the same time, the unique fixation mechanism may cause the distal end of the lead (tip) to be implanted away from the apical region of the heart, and therefore

the PCT may be slightly higher than the values observed in other Quadripolar LV leads. Therefore, we simulated the lead pacing threshold values based on the Attain Performa IDE study data, but excluding the PCT values collected at the most distal electrode. The simulation estimated that 89% of the subjects will achieve this endpoint (Figure 6).

Figure 6: Simulated PCT Distribution

Statistical Analysis Methods

All subjects with valid pacing thresholds measured at the 6 month follow-up visit will be included in this analysis. The proportion of subjects having at least one LV lead pacing vector with voltage thresholds less than or equal to 2.5V (with absence of PNS at 5.0 V) will be calculated. The lower bound of the 1-sided 97.5% Confidence Interval will be calculated using the Exact binomial method. Any subject in which no valid pacing threshold value is measured or who has an unable-to-capture result via all LV lead pacing vectors will be reviewed and adjudicated for a possible lead related AE but will not be included for this evaluation if the occurrence is deemed to be a system related event (e.g. lead dislodgement). However, this event may be counted against the safety primary endpoint based on the CEC's final classification.

Sample Size

The primary efficacy endpoint will be analyzed using the Exact binomial method. In order to preserve the overall study power, a type II error less than 10% was used for the sample size calculation. A sample size of 145 subjects achieves 91% power to detect a difference of 0.1 using a one-sided binomial test at a target significance level of 0.025. These results assume that the population proportion under the null hypothesis is 80%, with an expected proportion of 90%.

Determination of Patients / Data for Analysis

All subjects enrolled into this study satisfying the following conditions will be included in this analysis:

- Successfully implanted with a Medtronic Quad CRT-P or CRT-D device and Attain Stability Quad MRI SureScan LV Lead (Model 4798)
- Completed 6-month follow-up visit
- Initially implanted Attain Stability Quad MRI SureScan LV Lead (Model 4798) is active at the 6-month follow-up visit
- At least one available and valid pacing threshold at the 6-month follow-up visit

19.1.3. Primary Efficacy Objective # 2

Objective

The Attain Stability Quad lead will meet the second primary efficacy objective if the proportion of subjects with at least one additional (or second) LV lead pacing vector having a pacing capture threshold less than or equal to 4.0 V at 0.5ms pulse width (with absence of PNS at 5.0 V) at 6 months post-implant is greater than 80% (i.e., the one-sided 97.5% lower confidence bound must be greater than 80%).

Hypothesis

$H_0: P_{2-6\text{-month}} \leq 80\%$

$H_A: P_{2-6\text{-month}} > 80\%$,

where $P_{2-6\text{-month}}$ is the proportion of subjects with at least one additional LV lead pacing vector with pacing voltage thresholds $\leq 4.0V$ at 0.5ms (with absence of PNS at 5.0 V) at 6 months post-implant follow-up visit.

Endpoint Justification

The Attain Stability Quad MRI SureScan LV Lead (Model 4798) has 16 LV programmable pacing vectors . Subjects may have the pacing configuration programmed or reprogrammed at each clinic visit. A pacing threshold of 4.0 V (with absence of PNS at 5.0 V) will allow an adequate safety margin for programming LV pacing output. The maximum pacing amplitude of the CRT-P or CRT-D devices capable of programming pacing output to any LV lead pacing vector is 8.0V. In actual clinical practice, a less than 3V safety margin is used for the programmed LV lead pacing output in 99% of the patients.

Statistical Analysis Methods

The efficacy endpoint #2 will be analyzed using the Exact binomial method. The proportion of subjects with at least 2 LV lead pacing vectors having voltage thresholds less than or equal to 4.0V at 0.5ms (with absence of PNS at 5.0 V) will be calculated. The lower bound of the 1-sided 97.5% Confidence Interval will be calculated using the Exact binomial method. Any subject in which no valid pacing threshold values are measured or with an Unable-to-capture result via all LV lead pacing vectors will be reviewed and adjudicated for possible lead related complications, and therefore may be counted against the study safety endpoint. However, it will be counted as a failure if there is not any additional LV lead pacing vectors (excluding the vector that is already include for the efficacy endpoint #1) are unable to capture with no lead related events reported.

Sample Size

The Attain Performa Model 4298 LV lead observed 97.7% subjects who were able to obtain a non-programmed pacing vector with PCT less than or equal to 4 volts (with absence of PNS at 5.0 V). A sample size of 50 subjects completing the 6 month visit achieves 98% power to detect a difference of

0.18 using a one-sided binomial test at a target significance level of 0.025. These results assume that the population proportion under the null hypothesis is 80%, with the expected proportion of 97%.

Determination of Patients / Data for Analysis

All subjects enrolled into this study satisfying the following conditions will be included in this analysis:

- Successfully implanted with a Medtronic Quad CRT-P or CRT-D device and Attain Stability Quad MRI SureScan LV Lead (Model 4798)
- Completed 6-month follow-up visit
- Initially implanted Attain Stability Quad MRI SureScan LV Lead (Model 4798) lead is active at the 6-month follow-up visit
- At least one available and valid pacing threshold at the 6-month follow-up visit. In the event a subject failed to provide more than one valid pacing threshold value, that subject will be considered as not having at least one additional LV lead pacing with PCT \leq 4.0V at 0.5ms at 6 months post-implant follow-up visit

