Cognizant Technology Solutions [name] United States Direct [contact] Direct [contact]	Review of electronic case report forms and management of discrepancies

3. Version History

Version	Summary of Changes	Author(s)/Title
1.0	
 ○ Initial Release 	
[name], Principal Clinical Research Specialist
 
[name], Associate Clinical Research Specialist
 
[name], Principal Customer Specialist
 
[name], Senior Principal Statistician
 
[name], Senior Statistician

2.0	
 ○ Added slitting information for Implant analyzer PCT at synopsis and table 8 ○ Remote visits: 
 ▪ Changed wording to clarify required actions ▪ Removed manual PCT test ▪ Deleted rationale for final vector programmed ○ Recurring 6 mth FU: 
 ▪ Removed PNS test ▪ Removed Patient Global Assessment ○ System Modification 
 ▪ Reduced electrical testing requirements ○ Patient Global Assessment 
 ▪ Added to Glossary ▪ Removed from Baseline and 3 month visits ○ Vectors 
 ▪ Added additional 4 CRT-P vectors (LV to Can) throughout ○ Investigator Lead Handling Assessment 
 ▪ Added to Implant visit ○ Adjusted # of participating centers ○ Updated exclusion criteria #2 ○ Updates to grammar, version ,and footers 	
[name], Principal Clinical Research Specialist
 
[name], Associate Clinical Research Specialist

3.0	
○ Modified Primary Efficacy objectives/endpoints to include PNS testing○ Added reference to inclusion criteria that US patients should meet CRT device indications per the HRS/ACC/AHA guidelines○ Added reference to exclusion criteria that subjects with significant allergy to contrast dye will be excluded○ Added statement that EU will be full ISO 14155 compliant○ Broadened the 3rd secondary endpoint definition to include summary statistics on all PCTs and lead impedances collected	[name], Principal Clinical Research Specialist
-----	--	--

4. Investigator Statement

Investigators will be provided with a separate investigator agreement to document their obligation and commitment with respect to study conduct.

5. Index

1.	Sponsor Contact	3
2.	CROs/Core Laboratories	4
3.	Version History	5

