The Attain Performa Model 4298 LV lead observed 97.7% subjects who were able to obtain a non-programmed pacing vector with PCT less than or equal to 4 volts. A sample size of 50 subjects completing the 6 month visit achieves 98% power to detect a difference of 0.18 using a one-sided binomial test at a target significance level of 0.025. These results assume that the population proportion under the null hypothesis is 80%, with the expected proportion of 97%.

Determination of Patients / Data for Analysis

All subjects enrolled into this study satisfying the following conditions will be included in this analysis:

- Successfully implanted with a Medtronic Quad CRT-P or CRT-D device and Attain Stability Quad MRI SureScan LV Lead (Model 4798)
- Completed 6-month follow-up visit
- Initially implanted Attain Stability Quad MRI SureScan LV Lead (Model 4798) lead is active at the 6-month follow-up visit
- At least one available and valid pacing threshold at the 6-month follow-up visit. In the event a subject failed to provide more than one valid pacing threshold value, that subject will be considered as not having at least one additional LV lead pacing with PCT \leq 4.0V at 0.5ms at 6 months post-implant follow-up visit

19.2. Secondary Objectives**19.2.1. Secondary Objective # 1****Objective - Implant procedure related information: success rate, implant related times**

The Attain Stability Quad LV lead implant success rate will be estimated as the number of subjects with Attain Stability Quad MRI SureScan LV Lead (Model 4798) successfully implanted divided by the total number of subjects who had a Attain Stability Quad MRI SureScan LV Lead (Model 4798) implant attempt. A 2-sided 95% Confidence Interval will be calculated using the Exact Binomial method.

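### Efficacy objective #1 now requires absence of PNS, but its expected rate rests on a threshold-only simulation (89%), and the power statement assumes 90%

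*Protocol*

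**What the plan says.** The version history records for version 3.0: "Modified Primary Efficacy objectives/endpoints to include PNS testing". Accordingly, the objective in Section 19.1.2 is a PCT "less than or equal to 2.5 V at 0.5ms pulse width (with absence of PNS at 5.0 V"), in at least one vector at 6 months, with a lower 97.5% bound above 80%.

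The endpoint justification in the same section gives the basis of the expected rate: "we simulated the lead pacing threshold values based on the Attain Performa IDE study data", leaving out values from the most distal electrode. It concludes: "The simulation estimated that 89% of the subjects will achieve this endpoint (Figure 6"). Figure 6 is titled as a simulated PCT distribution. No PNS input is mentioned.

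The sample-size paragraph asks for a type II error below 10% and states: "A sample size of 145 subjects achieves 91% power to detect a difference of 0.1". It adds: "These results assume that the population proportion under the null hypothesis is 80%, with an expected proportion of 90" percent.

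The version 2.0 text, reproduced in the same document, defines the endpoint by threshold alone. It carries the same 89%, 90%, 145 and 91%.

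For objective #2 (Section 19.1.3), the predecessor lead "observed 97.7% subjects who were able to obtain a non-programmed pacing vector with PCT less than or equal to 4 volts". The current text follows this with the PNS condition. In version 2.0 the same figure stands without it: "who were able to obtain a non-programmed pacing vector with PCT less than or equal to 4 volts. A sample size of 50".

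**The concern.** A subject who meets the PCT limit on some vector succeeds under the current objective #1 only if such a vector is also free of PNS at 5.0 V. On any one data set, the proportion meeting both conditions cannot exceed the proportion meeting the first. It may equal it or fall below it. A simulation of thresholds alone therefore cannot say what share will achieve this endpoint as now defined.

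The section also disagrees with itself on a point unrelated to PNS. It estimates 89% and then computes power at 90%.

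Both efficacy objectives must be met together, so any shortfall in #1 carries straight through to the efficacy claim. At stake is whether the power quoted for #1 has a documented basis for the endpoint under test.

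**Working it through.** **Inputs**
- Null proportion 80%, one-sided 0.025, exact binomial, n=145, expected 90%, type II error below 10% (Section 19.1.2).
- Simulated rate 89% (Section 19.1.2, endpoint justification).
- 400 subjects needed at 6 months and 471 enrolled (Table 18). Up to 37 historical subjects may be borrowed for secondary objective #2, and Section 19.2.2 gives a range of 363 to 400.
- PNS loss: no rate is given in the protocol. A net loss of 0 to 5 percentage points from 89% is assumed here.

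**Formula**
r is the smallest count with P(X ≥ r | n, 0.80) ≤ 0.025. Power is P(X ≥ r | n, p1). This is equivalent to requiring the exact lower bound to exceed 80%.

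**Step 1: the protocol's figure.** n=145 gives r=126, with actual alpha 0.0204. Power at 0.90 is 0.913. The stated 91% is reproduced.

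**Step 2: the protocol's own 89%.** With the same n and r, power is 0.828. Type II error is 1 − 0.828 = 0.172, above the 0.10 limit before any PNS loss. Power of 90% at n=145 needs a true rate of about 89.8%.

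**Step 3: the size the study will have.** I read 363 to 400 as subjects at 6 months, because 400 − 37 = 363 and Table 18 places the 400 at 6 months. The critical counts are r=306 at n=363 and r=336 at n=400.

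| Joint success rate | Assumed PNS loss from 89% | Power, n=363 | Power, n=400 |
|---|---|---|---|
| 89% | 0 points | 99.8% | 99.9% |
| 87% | 2 points | 94.3% | 96.6% |
| 86% | 3 points | 84.4% | 88.8% |
| 85% | 4 points | 67.8% | 73.9% |
| 84% | 5 points | 47.3% | 53.3% |

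The joint rate that gives 90% power is about 86.5% at n=363 and 86.1% at n=400.

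Section 19.2.2 literally calls the 363 to 400 enrolled. On that reading, 400 × 0.85 = 340 completers, and power is 99.6% at 89%, 93.0% at 87% and 82.3% at 86%. The picture is similar.

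**Step 4: objective #2.** n=50 gives r=46, with actual alpha 0.0185. Power at 0.97 is 0.983, so the stated 98% is reproduced. The stated difference of 0.18 does not match its own inputs: 0.97 − 0.80 = 0.17.

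**The case against.** The strongest reply is that the 145 is not the size of this trial. Secondary objective #2 sets the study at 400 subjects at 6 months. There, objective #1 has 99.9% power at 89%, and the gap between 89% and 90% has no practical effect. This stands, and it limits the point to documentation plus a conditional risk. A reader might infer from n=145, where power is 58% at 87%, that the trial is underpowered. The planned size does not support that.

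Second, the 91% and 98% are arithmetically right for 90% and 97%. This also stands. The fault lies in the basis of the 90%, not in the calculation.

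Third, the simulation discards the distal electrode, which may make 89% conservative, and a subject needs only one qualifying vector of sixteen, so the PNS loss could be small. Both are fair. They bear on the true rate, but neither puts PNS into the simulation. The 89% is a ceiling on what that simulation supports, not on the performance of the lead.

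Fourth, a reader might infer that objective #2 has the same defect, since the 97.7% is identical in both versions. The current text states it as PNS-inclusive. PNS may have cost no subject, version 2.0 may have described the figure loosely, or the label may have been added later. The protocol cannot settle which.

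Table 24 might also be read as supplying a PNS rate: device stimulation issues in 349 of 3,246 subjects, 10.75%. It is a pooled adverse-event term across several studies, not the share of qualifying vectors with PNS at 5.0 V, so it gives no usable rate here.

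**Conclusion.** The point holds for objective #1. The 89% is a threshold-only estimate, unchanged from the version whose endpoint had no PNS condition, and it is presented as an estimate for the current endpoint. The power statement then uses 90%, which exceeds even that. At the stated n=145, the protocol's own estimate gives 83% power, short of the 90% implied by its type II error limit.

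In practice the exposure is modest. At 363 to 400 completers, power stays at or above 90% unless the joint rate is below about 86.5% (n=363) or 86.1% (n=400), that is, unless PNS costs about 2.5 to 3 points from 89%. At a loss of 5 points it would be 47% to 53%. The size of the loss is an assumption, since the protocol gives no figure.

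Two further inferences are not supported. The 98% power for objective #2 is not shown to be wrong. Nor does objective #1 have the narrowest design margin of the primary objectives: 89% against 80% is 9 points, while safety is planned on 94% against 87%, which is 7.

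**What to change.** For objective #1:
- Re-derive the expected rate from the predecessor data under the joint criterion (PCT ≤ 2.5 V and no PNS at 5.0 V on the same vector), keeping the exclusion of the distal electrode if still wanted.
- Use that rate in the power statement in place of 90%.
- Restate power at 363 to 400 completers, with rows for an assumed PNS loss of 0 to 5 points as in the table above.
- If the predecessor data cannot yield PNS at 5.0 V by vector, say so, label the 89% as threshold-only, and rely on the range.

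For objective #2:
- Confirm the source of the 97.7% and whether it includes the PNS condition.
- Correct the difference from 0.18 to 0.17.

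The cost is a re-analysis of data the sponsor should hold (the current text already reports a PNS-inclusive figure for Model 4298) and a few sentences of protocol text. No change of design or enrolment follows unless the joint rate turns out to be about 86% or lower. The quoted power for #1 may become less favourable than the current text suggests.
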